kg	Kilograms
LDH	Lactate Dehydrogenase
LLN	Lower Limit of Normal
m	Meters
MAR	Missing at Random
MCH	Mean Corpuscular Hemoglobin
MCHC	Mean Corpuscular Hemoglobin Concentration
MCV	Mean Corpuscular Volume
MedDRA	Medical Dictionary for Regulatory Activities
mg	Milligram
mg/d	Milligrams per day
MI	Multiple Imputation
MITT	Modified intent to treat
mL/min	Milliliters per minute

Abbreviation	Explanation
mmHg	Millimeters of Mercury
MMRM	Mixed model repeated measurement
MN	Miettinen-Nurminen
MS	Multiple sclerosis
MSWS-12	Multiple Sclerosis Walking Scale-12
N/A	Not Applicable
NMAR	Not Missing at Random
OLE	Open-label extension
PCS	Potentially clinically significant
PP	Per-protocol
PT	Preferred Term
RBC	Red Blood Cell
s, sec	Seconds
SAP	Statistical Analysis Plan
SI	International Standard
SOC	System organ class
T25FW	Timed 25-Foot Walk
TEAE	Treatment-emergent adverse event
TUG	Timed Up and Go
ULN	Upper Limit of Normal
WBC	White blood cell(s); leukocyte(s)
WHO	World Health Organization

Adamas Pharmaceuticals, Inc
ADS-AMT-MS301

Statistical Analysis Plan, Version 2.0
Date Issued: 05Dec2019

1. Introduction

This statistical analysis plan (SAP) is based upon Section 14 (Statistics) of the Protocol dated 28 February 2018 / Amendment 1.0 and is prepared in compliance with International Conference on Harmonization (ICH) E9. Furthermore, this SAP describes the analyses and data presentations for the final analysis of data collected for Study ADS-AMT-MS301.

Adamas is developing ADS-5102, an extended-release (ER) capsule formulation of amantadine hydrochloride (HCl), as a treatment to improve walking in patients with multiple sclerosis (MS).

2. Objectives

2.1. Primary

To evaluate the efficacy of 274 mg ADS-5102 in subjects with multiple sclerosis (MS) with walking impairment as measured by the Timed 25-foot Walk (T25FW, feet/second) at Week 16.

2.2. Secondary

2.2.1. Key

- To evaluate the efficacy of 274 mg ADS-5102 in subjects with MS and walking impairment as measured by the Timed Up and Go (TUG) test (s), and the 2-Minute Walk Test (2MWT) (m) at Week 16.
- To evaluate the efficacy of 137 mg ADS-5102 in subjects with MS and walking impairment as measured by the T25FW (feet/second), the TUG test (s), and the 2MWT (m) at Week 16.

2.2.2. Supportive

- To evaluate the efficacy of 274 mg ADS-5102 and 137 mg ADS-5102 in subjects with MS and walking impairment as measured by the T25FW (s), the TUG (s), and the 2MWT (m) across all study visits.
- To evaluate the efficacy of 274 mg ADS-5102 and 137 mg ADS-5102 in subjects with MS and walking impairment as measured by the Multiple Sclerosis Walking Scale-12 (MSWS-12) in subjects treated with 274 mg ADS-5102 and subjects treated with 137 mg ADS-5102.

2.2.3. Safety

- To evaluate the safety and tolerability of 274 mg and 137 mg of ADS-5102 in subjects with MS and walking impairment.

3. Investigational Plan

3.1. Overall Study Design and Plan

This is a multicenter, 3-arm, randomized, placebo-controlled, double-blind, parallel-group study of ADS-5102 (amantadine ER capsules) in MS subjects with walking impairment, incorporating a Single-Blind Placebo Run-In Period prior to randomization, and forced up-titration for the high-dose group.

All subjects will have received a stable regimen of MS medications, both disease modifying and symptomatic, for at least 30 days prior to screening, and will continue the same doses and regimens for the duration of their study participation, to the extent compatible with good neurological care. Subjects will not have used amantadine, dalfampridine, or any 4-AP or 2,4-diaminopyridine (2,4-DAP) preparation within 30 days prior to screening.

Consented subjects who complete the up to 3-week screening period will undergo a 4-week Single-Blind Placebo Run-In Period during which they will take their dose of 2 placebo capsules once daily at bedtime.

Subjects who complete the Single-Blind Placebo Run-In Period and continue to meet study eligibility criteria will be randomized with equal probability to 1 of 3 treatment groups: placebo or ADS-5102 at a final dosage of either 137 or 274 mg/d (treatment groups are identified by their final dosage). Study drug will be administered as 2 capsules once daily at bedtime.

Subjects who are randomized to placebo will receive placebo capsules throughout the 12-week Double-Blind Treatment Period, including the 2-week forced titration and 10-week maintenance phases.

Subjects who are randomized to 274 mg of ADS-5102 will receive 137 mg for the first week (Week 1 of the forced titration phase of the Double-Blind Treatment Period), 205.5 mg for the second week (Week 2 of the forced titration phase of the Double-Blind Treatment Period), and 274 mg for the remaining 10 weeks of the 12-week Double-Blind Treatment Period.

Subjects will return to the clinic for safety and efficacy assessments at Week 0 and Week 2 prior to randomization and at Weeks 4 (randomization and baseline visit), 6 (only safety), 8, 12, and 16 after randomization. In addition, telephone visits for safety assessments will be conducted at Weeks 5 and 7. Subjects who withdraw from the study before Week 16 will have an early termination visit that includes safety follow-up and efficacy assessments, as appropriate.

Subjects who complete 12 weeks of double-blind treatment (16 weeks total treatment, including placebo run-in) without significant protocol deviations, as assessed by the investigator and the sponsor, will be eligible to enter an optional open-label extension (OLE) study, protocol ADS-AMT-MS303. The Week 16 visit of Study ADS-AMT-MS301 will serve as the first study visit of Study ADS-AMT-MS303 for those subjects who consent to participate.

Subjects who complete 12 weeks of double-blind treatment (16 weeks total treatment, including placebo run-in) but elect not to participate in the OLE study will return to the clinic for a final

post-treatment safety and efficacy assessment 2 weeks after their Week 16 visit (Week 18), i.e., after being off treatment for approximately 2 weeks.

The End of Study (EOS) is defined as when a subject completes the Week 16 visit (if electing to enter the OLE study) or the Safety Follow-Up Visit (Week 18) (if electing not to enter the OLE study).

All study visits and efficacy assessments should be scheduled at approximately the same time of day for an individual subject. To the extent practicable, study visits and efficacy assessments should be scheduled to occur when a subject is not likely to be experiencing acute side effects from a concomitant medication (e.g., flu-like side effects following interferon-beta injection). Efficacy assessments should be conducted in the following sequence: MSWS-12; T25FW; TUG; 2MWT. Subjects using an assistive device during the walking assessments at Screening should use the same assistive device for all subsequent walking tests. Each efficacy assessment for an individual should be performed by the same clinical rater, if possible.

Adverse events and concomitant medications will be recorded beginning with the first dose of study drug and continuing through the last study visit.

The schedule of assessments is provided in [Appendix 14.1](#).

3.2. Study Endpoints

3.2.1. Primary

The primary efficacy endpoint is the proportion of responders in each treatment group, where a responder is defined as a subject who has a $\geq 20\%$ increase from Baseline to Week 16 in walking speed measured using the T25FW (average of two measurements 5 minutes apart), in the Intent-to-Treat (ITT) analyses set. Subjects who do not have a Week 16 assessment will be classified as having an indeterminate outcome and will be included in the denominator (i.e., they will be treated as de-facto non-responders). If a subject has not completed two walking tests, then the result for the one T25FW will be used.

3.2.2. Secondary

3.2.2.1. Key

The key secondary endpoints listed below will be used for comparisons between treatment groups for which inferential statistics, with appropriate control of the Type I error rate, will be used.

- The mean change from baseline at Week 16 in the T25FW (feet/second)
- The mean change from baseline at Week 16 in the TUG (s)
- The mean change from baseline at Week 16 in the 2MWT (m)

3.2.2.2. Supportive

The following endpoints will be used for supportive comparisons among treatment groups.

- Mean changes from baseline in the T25FW (feet/second) at Weeks 8 and 12
- Mean changes from baseline in the T25FW (s) at Weeks 8, 12 and 16
- Mean changes from baseline in the TUG (s) at Weeks 8 and 12
- Mean changes from baseline in the 2MWT (m) at Weeks 8 and 12

3.2.2.3. Safety

Safety endpoints will include incidence of subjects with adverse events data, potentially clinically significant changes in laboratory data, and changes in the Columbia-Suicide Severity Rating Scale (C-SSRS) data.

4. Treatments

Study treatments consist of an oral formulation of extended release (ER) amantadine HCl (ADS-5102) and a placebo control. The clinical supplies will include 137 mg and 68.5 mg ADS-5102 capsules and matching placebo capsules. All capsules provided during the study are indistinguishable in size and appearance.

The dosing regimens for the 2 active treatment arms are:

- 137 mg/d (1 x 137 mg capsule + 1 placebo capsule) for 12 weeks for the 137 mg ADS-5102 group
- 137 mg/d for 1 week (1 x 137 mg capsule + 1 placebo capsule), followed by 205.5 mg/d (1 x 137 mg capsule + 1 x 68.5 mg capsule) for 1 week, followed by 274 mg/d (2 x 137 mg capsules) for 10 weeks for the 274 mg ADS-5102 group

Placebo capsules will be administered orally as 2 capsules once daily at bedtime for the 4-week Single-Blind Placebo Run-In Period for all subjects and for the 12-week Double-Blind Treatment Period for subjects randomized to the placebo arm.

4.1. Dose Adjustment/Modifications

Dose Adjustment for Renal Impairment

Subjects whose estimated glomerular filtration rate (eGFR) falls below 60 mL/min/1.73 m², confirmed by repeat testing, should discontinue study drug. These subjects should be encouraged to complete study visits per the protocol.

Dose Adjustment for Adverse Events

Study drug may only be withheld for the evaluation or treatment of an AE. If, in the judgement of the investigator, study drug should be withheld for the evaluation or treatment of an AE, the investigator may have the subject do so for up to 3 consecutive days, and is then to have the subject resume dosing at the same dose level. If, in the judgement of the investigator, study drug needs to be withheld for more than 3 consecutive days, the investigator must contact one of the study's Medical Monitors to determine whether drug may be withheld for a longer period or the subject should be permanently discontinued from study drug. Study drug may not be down-

titrated. This procedure applies to the withholding of study drug throughout the study with the exception of the titration phase of the Double-Blind Treatment Period.

In the special case of study drug being withheld for the evaluation or treatment of an AE occurring during the titration phase of the Double-Blind Treatment Period (i.e., Week 4 to Week 6), the investigator may have the subject do so for up to 3 consecutive days, and is then to have the subject resume dosing at the same dose level. The subject is to finish the remaining capsules in the blister card, i.e., including the 2-dose overage. The subject must return to the clinic to receive his or her next blister pack without missing any additional doses. If, in the judgement of the investigator, study drug needs to be withheld for more than 3 consecutive days, the subject is to be permanently discontinued from study drug.

5. General Statistical Considerations

5.1. Randomization, Stratification, and Blinding

A subject is considered randomized at Baseline/Week 4, when the site confirms the randomization event via a centralized randomization system (interactive web response system [IWRS]).

Following completion of the 4-week Single-Blind Placebo Run-in Period, consented subjects who continue to meet eligibility criteria will be randomly assigned in equal probability to 1 of 3 treatment groups: placebo, 137 mg ADS-5102, or 274 mg ADS 5102. No stratifications are being utilized in the randomization design.

The identity of the treatment assigned to individual subjects can be revealed in an emergency only. A subject's treatment assignment should only be unblinded when knowledge of treatment is essential for the safety of the subject. Emergency unblinding will be considered a major protocol deviation.

5.2. Sample Size

Based on the results from the Phase 2 study, responder rates of 24% and 33% were observed at Week 4 for subjects treated with placebo and 274 mg ADS-5102, respectively, in the modified intent-to-treat (MITT) analysis set. In the present study, it is anticipated that the placebo response rate at Week 16 will be no greater than 20% and the response rate among subjects treated with 274 mg or 137 mg ADS-5102 will be at least 33%. Using these estimates, 180 randomized subjects per active treatment group and placebo group will be needed for the test of differences in proportions (Farrington-Manning approach for the Miettinen-Nurminen [MN] test) to have 80% power at the 2-sided 5% significance level to detect this 13% difference favoring ADS-5102. Assuming a 5% dropout rate during the 4-week Single-Blind Placebo Run-In Period, 570 subjects will be enrolled in the study to randomize 540.

For this sample size of 180 randomized subjects per group, power will be at least 80% to detect treatment differences (ADS-5102 versus placebo) of -2.7 seconds and 5.0 meters in the changes from baseline at Week 16 in the TUG test and 2MWT when the standard deviations of the

change from baseline are no greater than 6.0 sec and 14.9 meters, respectively, and the dropout rate is not greater than 20%.

5.3. Analysis Set

5.3.1. All Enrolled

The all enrolled set will include all subjects who signed the study informed consent form and entered the placebo run-in period.

5.3.2. Intent-to-Treat (ITT) Set

The intent-to-treat (ITT) analysis set will include all randomized subjects who receive at least one dose of double-blind study drug, and will be analyzed according to the randomized treatment assignment. This population will be used for the efficacy analyses including the analyses of primary and key secondary endpoints.

5.3.3. Per Protocol (PP) Set

The per-protocol (PP) analysis set will include all randomized and dosed subjects who provide Week 16 T25FW data and do not have any major protocol deviations as outlined in [Section 6.2](#) that could confound this assessment. These deviations will be determined prior to unblinding and database lock. This population will also be used for select efficacy analyses. Subjects in the PP set will be analyzed according to the randomized treatment assignment.

5.3.4. Safety Set

The safety analysis set will include all randomized subjects who receive at least one dose of double-blind study drug, and will be analyzed according to the treatment actually received. If there are no treatment misallocations, this population will be identical to the ITT analysis set.

5.4. Baseline

For endpoints based on the T25FW, Baseline will be defined as the average of up to two separate visit averages (each based on up to two measurements taken five minutes apart) collected at Weeks 2 and 4 (prior to randomization). If one of the two T25FW Baselines values is missing, then Baseline will be defined as the last non-missing measurement prior to or on the date of randomization.

For endpoints based on the TUG, 2MWT, and MSWS-12, Baseline will be defined as the average of up to two separate measurements collected at Weeks 2 and 4 (prior to randomization). If one of the two TUG, 2MWT and/or MSWS-12 Baselines values is missing, Baseline will be defined as the last non-missing measurement prior to or on the date of randomization.

For C-SSRS analyses, the questionnaire three-year history data obtained during the Screening visit will be considered Baseline.

For all other endpoints, Baseline is defined as the last non-missing measurement prior to or on the date of randomization.

5.5. Study Completion

Study completion is defined as study participation through the Week 16 Visit and rollover into OLE, or completion of a Safety Follow-Up Visit.

5.6. Study Day

Study Day 1 will correspond with the date of first dose of double-blind study drug. Study day will be calculated as follows:

If the Date of Interest < First Dose Date of Double-Blind Study Drug then,
$$\text{Study Day} = (\text{Date of Interest} - \text{Date of Randomization})$$

If the Date of Interest \geq First Dose Date of Double-Blind Study Drug then,
$$\text{Study Day} = \text{Date of Interest} - \text{Date of Randomization} + 1$$

For subjects that are never treated with double-blind study drug, study day will not be calculated.

5.7. Standard Conversions

The following conversions will be used:

1 Year = 365.25 days

1 Month = 30 days

1 Week = 7 days

1 Meter = 39.37 inches

5.8. Unscheduled Visits

Data collected at unscheduled visits will be displayed in data listings and used to calculate maximum/minimum values, as applicable, but will not be displayed in summaries presented by study visit.

5.9. Visit Windowing

No programmatic visit windowing will be implemented.

5.10. Significance Level

Unless otherwise specified, all testing of statistical significance will be 2-sided, and a treatment difference resulting in a p-value less than or equal to 0.05 will be considered statistically significant. Similarly, all confidence intervals will be two-sided 95% confidence intervals.

5.11. Data Imputation

Unless otherwise specified, all available efficacy and safety data will be included in data listings and tabulations. Prior to database lock, critical data that are potentially spurious or erroneous will be examined and queried according to standard data management operation procedures.

For the efficacy analyses of responder rates, a subject with missing data will be defined as a non-responder. For all other endpoints, missing data will be treated as missing and no data imputations will be applied, unless otherwise specified. See [Section 9.2.1](#) for sensitivity analyses concerning the missing data assumptions.

5.11.1. Missing/Partial Dates in Concomitant Medications

Concomitant medications with start dates that are completely or partially missing will be analyzed as follows:

- If month and year are known, but day is missing, then impute day to first of the month
- If year is known, but day and month are missing, then 1st of January of the year will be imputed
- If the start date is completely missing, then impute date to first dose date of double-blind study drug
- Should any of the previous concomitant medication start dates created come after the complete medication stop date provided, the medication stop date will be used instead

Concomitant medications with stop dates that are completely or partially missing will be analyzed as follows:

- If “ongoing” is checked, no imputation is necessary
- If month and year are known but day is missing, the last day of the month will be imputed
- If year is known, but day and month are missing,
 - If YYYY < year of last dose of double-blind study drug, then 31st of December will be imputed
 - If YYYY = year of last dose of double-blind study drug, then the last dose date of study drug will be imputed
 - If YYYY > year of last dose of double-blind study drug, then 1st of January will be imputed
- If the stop date is completely missing, then impute date to last dose date of double-blind study drug
- If subject dies, then use death date for concomitant medication stop date. After the imputation, all imputed stop dates will be checked against the corresponding start dates to ensure the stop date does not come before the start date. If the imputed stop date is prior to the start date, then the start date will be used.

5.11.2. Missing/Partial Dates in Adverse Events

Adverse events with start dates that are completely or partially missing will be imputed as follows:

- If month and year are known but day is missing
 - If month and year are the same as month and year of first dose date of double-blind study drug, then impute to first dose date of double-blind study drug
 - If month and year are different than month and year of first dose date of double-blind study drug, then impute to first of the month
- If year is known but day and month are missing
 - If year is same as year of first dose date of double-blind study drug, then first dose date of double-blind study drug will be used instead
 - If year is different than year of first dose date of double-blind study drug, then 1st of January of the year will be imputed
- If the start date is completely missing, then it will be imputed with first dose date of double-blind study drug

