9.4. Administration

Table 3: Randomization Groups for Study ADS-AMT-MS301

TREATMENT GROUP			
	274 mg ADS-5102	137 mg ADS-5102	Placebo
Single-Blind Placebo Run-In Period			
Week 0 to Week 4	2 x placebo capsules	2 x placebo capsules	2 x placebo capsules
Double-Blind Treatment Period, Forced Titration Phase			
Week 4 to Week 5	1 x 137 mg ADS-5102 capsule 1 x placebo capsule	1 x 137 mg ADS-5102 capsule 1 x placebo capsule	2 x placebo capsules
Week 5 to Week 6	1 x 137 mg ADS-5102 capsule 1 x 68.5 mg ADS-5102 capsule	1 x 137 mg ADS-5102 capsule 1 x placebo capsule	2 x placebo capsules
Double-Blind Treatment Period, Maintenance Phase			
Week 6 to Week 16	2 x 137 mg ADS-5102 capsule	1 x 137 mg ADS-5102 capsule 1 x placebo capsule	2 x placebo capsules

Each dose will be administered as 2 oral capsules once daily at bedtime.

Capsules are to be swallowed intact, and can be taken with any nonalcoholic beverage, with or without food.

While taking study drug, concomitant use with alcohol is not recommended, as it may increase the potential for CNS effects such as dizziness, confusion, lightheadedness, and orthostatic hypotension and may result in dose-dumping

Dosing will continue through Week 16.

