10.1. Adverse Events

Adverse events (AE) will be recorded starting from the date/time of first dose during the Single-Blind Placebo Run-In Period through the End of Study (EOS) Visit. The time periods of AE

recording will be divided into AEs with onset during the Single-Blind Placebo Run-In Period and AEs with onset during the Double-Blind Treatment Period.

A Treatment-Emergent Adverse Event (TEAE) is defined as an adverse event that begins or worsens in severity on or after the date of randomization.

Incidence of TEAEs during the Double-Blind Treatment Period (as well as number and percentage of subjects with TEAEs) will be tabulated according to Medical Dictionary for Regulatory Activities (MedDRA) by system organ class (SOC) and preferred term (PT) and will include the following categories:

- All TEAEs
- Most Commonly Reported TEAEs ($\geq 5\%$ in any treatment group) (by PT only)
- TEAEs by Relatedness to Study Drug
- TEAEs by Severity
- TEAEs Leading to Study Drug Discontinuation
- Serious TEAEs Leading to Study Drug Discontinuation by Relatedness to Study Drug
- Serious TEAEs by Relatedness to Study Drug
- Study Drug-Related Serious TEAEs
- TEAEs of Special Interest

MedDRA dictionary Version 21.0 will be used for reporting and will be described in the relevant table and listing footnotes.

Subjects with the same AE more than once will have that event counted only once within each System organ class (SOC) and Preferred term (PT). Subjects with the same AE more than once will have the maximum intensity of that event counted within each SOC and once within each PT for summaries of severity.

SOCs and PTs within SOC will be presented by descending frequency based on the ADS-5102 274 mg and ADS-5102 137 mg groups combined.

An overall summary AE table will include the numbers and percentages of subjects who had at least one of each of the following: TEAE, serious TEAE, study drug-related TEAE, TEAE leading to study drug discontinuation, serious TEAE leading to study drug discontinuation, study drug-related serious TEAE, AE of special interest, or on-study death.

TEAEs that have missing severity will be classified in table summaries as severe. Similarly, TEAEs that have missing relationship to study drug will be classified in table summaries as related.

All AEs will be listed by subject and period.

The three AE categories listed below are considered adverse events of special interest (AESI):

- Suicidality
- Hallucinations

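### SAP 5.11.2 can impute an adverse event's onset later than its own stop date, making a resolved run-in event a TEAE; SAP 5.6 has a related study-day inconsistency

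*Combined protocol and SAP*

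**What the plan says.** SAP 5.11.2 has three branches that move an incomplete AE start date to the first double-blind dose date:

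- Day unknown: "If month and year are the same as month and year of first dose date of double-blind study drug".
- Only the year known: "If year is same as year of first dose date of double-blind study drug, then first dose date of double-blind study drug will be used".
- Nothing known: "If the start date is completely missing, then it will be imputed with first dose date of double-blind study drug".

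In the non-matching cases the start becomes the first of the stated month, or 1 January of the stated year. No branch refers to the AE stop date.

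SAP 5.11.1, immediately before, handles concomitant medications and does have that safeguard. Should an imputed start "come after the complete medication stop date provided, the medication stop date will be used instead".

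SAP 10.1 then defines a TEAE as "an adverse event that begins or worsens in severity on or after the date of randomization". SAP Section 11 lists the move from first double-blind dose to randomization date as a change from the protocol. Protocol 13.2.1 says events in the single-blind placebo run-in are to be captured but not treated as TEAEs, and protocol 14.5 equates TEAEs with events during the double-blind period.

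On study day, SAP 5.6 states: "Study Day 1 will correspond with the date of first dose of double-blind study drug". Both formulas below that sentence subtract the date of randomization.

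**The concern.** AE recording starts with the first run-in placebo dose, so the AE dataset holds four weeks of events that precede any double-blind drug. What separates them from TEAEs is the onset date. Where that date is incomplete, 5.11.2 supplies one that always falls on the treated side of the line, even when the record already contains a stop date proving that the event was over.

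Two things follow. The analysis dataset can hold an impossible record, with onset after resolution. And an event that the protocol excludes from the TEAE class can enter the TEAE tables. Because the medication rule has the check and the AE rule does not, this looks like an omission rather than a decision.

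The study-day wording is a separate defect of the same kind: the definition uses one anchor date and the formulas use another.

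**Working it through.** The plan gives no figure to reproduce here, so the check applies the rules as written.

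**1. A worked case (dates assumed).** Randomization and first double-blind dose are both on 20 August 2018, so the 28-day run-in is 23 July to 19 August. An AE is recorded with start August 2018, day unknown, and stop date 10 August 2018.

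- SAP 5.11.2: month and year match the first dose, so onset = 20 August.
- Stop minus onset = 10 − 20 = −10 days.
- SAP 10.1: 20 August is on or after randomization, so the event is a TEAE.
- With the 5.11.1 check applied: imputed start (20 August) is after stop (10 August), so onset = 10 August, before randomization, and the event stays in the run-in.

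**2. How many run-in days are exposed.** Inputs: a 28-day run-in (protocol 7.1); first dose assumed on the randomization date; first-dose dates assumed evenly spread over calendar 2018.

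*Day missing.* With first dose on day d of a month, min(d − 1, 28) run-in days share that month. Summed over the month:

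- 31-day month: (0 + 1 + … + 28) + 28 + 28 = 406 + 56 = 462
- 30-day month: 406 + 28 = 434
- 28-day month: 0 + 1 + … + 27 = 378

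Year total = 7 × 462 + 4 × 434 + 378 = 5,348. All run-in days = 365 × 28 = 10,220. Share = 5,348 / 10,220 = 52.3%.

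*Only year known.* First doses on days 1 to 28 of the year contribute 0 + 1 + … + 27 = 378. The other 337 dates contribute 337 × 28 = 9,436. Share = 9,814 / 10,220 = 96.0%.

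*Nothing known.* 100%.

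For assumed first-dose dates from April 2018 to September 2019 (548 dates) the first two shares are 52.4% and 97.4%.

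**3. The other direction.** An incomplete date for a true double-blind event becomes either the first-dose date or the first day of a later month or year. None of these precedes randomization, so 0% are lost. The misclassification runs one way only.

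**4. Illustrative size per arm of 180.** The documents give neither the run-in AE rate nor the share of incomplete dates. Assume 0.1 to 0.5 run-in AEs per subject, with 1% to 10% of them lacking the day:

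- Low: 180 × 0.1 × 0.01 × 0.523 = 0.09 events
- High: 180 × 0.5 × 0.10 × 0.523 = 4.7 events

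These count every event moved by the day-missing branch. Those with a stop date before randomization, which the check would correct, are a subset.

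**5. Effect on an arm contrast.** Assume true TEAE rates of 30% and 20%, with 1% of subjects per arm carrying a moved event:

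- 0.30 + 0.70 × 0.01 = 30.7%
- 0.20 + 0.80 × 0.01 = 20.8%
- Difference: 10.0 becomes 9.9 points. Ratio: 1.50 becomes 1.48.

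**6. Study day (SAP 5.6).** Let randomization be R.

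- First dose on R + 1: date R is before first dose, so R − R = Day 0. The first-dose date gives (R + 1) − R + 1 = Day 2. No date is Day 1.
- First dose on R: R − R + 1 = Day 1, as defined.

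The formulas fail only when the two dates differ.

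**The case against.** The strongest reply is that assigning an uncertain onset to treatment is the conventional, conservative choice in safety reporting, and that few dates will be uncertain: the CRF asks for onset date and time (protocol 13.1.1 and 13.2.1), and SAP 5.11 provides for querying suspect critical data before lock. Most of this stands. Conservatism, however, is a reason to default ambiguous dates, and an event with a stop date before randomization is not ambiguous. Querying does not cure the problem either, since the impossible order is created by the imputation.

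A reader might infer more than the documents support:

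- *That the TEAE tables do contain run-in events.* Only that they can. A run-in event with a complete start date before randomization is not moved unless it later worsens, and no count of incomplete dates is given.
- *That the drug–placebo contrast is materially diluted.* The effect is expected to be equal across arms and, on the assumptions above, is about a tenth of a percentage point. A subject who already has another TEAE adds nothing to overall incidence.
- *That the run-in's purpose in protocol 5.6 is undone.* That rationale concerns AE-prone subjects who stop during the run-in. They are never randomized and are outside the safety set (SAP 5.3.4), so no imputation rule brings their events back.
- *That the randomization-date anchor in SAP 10.1 is itself an error.* Dosing is at bedtime ("Each dose will be administered as 2 oral capsules once daily at bedtime", protocol 9.4), so an event earlier on the randomization date does count as a TEAE before any double-blind drug. But SAP Section 11 discloses this choice and it normally concerns part of one day. The documents do not show that the time of the first double-blind dose is recorded; SAP 8.2.1 works in dates.

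**Conclusion.** The point holds in a limited form. As written, SAP 5.11.2 can produce an AE onset after the AE's own stop date and can class as treatment-emergent an event that had ended before randomization, contrary to protocol 13.2.1. The exposed share of run-in days is about 52% when the day is missing, about 96% when only the year is known, and 100% when the date is wholly missing. These shares assume evenly spread first-dose dates and a first dose on the randomization date. The absolute number of events is unknown and probably small, no arm is favoured, and the efficacy analyses are not affected.

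The SAP 5.6 inconsistency is certain on the text, but changes a result only for subjects whose first double-blind dose is not on the randomization date. It plays no part in TEAE classification. Both defects are worth correcting because stated rules give wrong results and the correction is cheap.

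**What to change.** - **SAP 5.11.2:** add the check used in 5.11.1. If the imputed AE start falls after a complete AE stop date, use the stop date as the start. Events that ended before randomization then stay in the run-in; events without a complete stop date, or whose stop date does not settle the matter, keep the present default.
- **SAP 5.6:** subtract the first double-blind dose date in both formulas. In the case above, date R then becomes Day −1 and the first dose Day 1.
- **Optional, SAP 10.1:** where the CRF onset time and the first-dose time are both available, class events on the randomization date by whether they began before or after the first dose. Otherwise keep the disclosed randomization-date rule.

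The two main changes need a sentence or two of SAP text and minor programming, with no new data. The optional one depends on a dose time that the documents do not show to be collected. The downside is that TEAE counts may fall slightly.
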